9.5 Medical History

Medical history will be coded using the Medical Dictionary for Regulatory Activities (MedDRA V17.0 or higher). All medical history data will be provided in a listing.

9.6 Efficacy Analyses

Response of lesions and disease status will be assessed using standard RECIST v1.1 for the primary evaluation of response *and a study specific modified RECIST v1.1 referred to as immune related-RECIST v1.1 (irRECIST v1.1) for an exploratory evaluation (not implemented)*. Therefore, RECIST v1.1 will be used with the following adaptations (Appendix 1):

- Determination of progressive disease (PD) requires a confirmation of PD by imaging ≥ 4 weeks later. In order to confirm PD, both the initial lesion assessment and lesion assessment on the confirmatory scan must meet PD criteria ($\geq 20\%$ increase in sum of diameters).
- Continued treatment while awaiting radiologic confirmation of progression is encouraged if the patient is stable.

Patients that are deemed clinically unstable are not required to have repeat imaging for the confirmation of PD.

Objective response rate (ORR) and disease control rate (DCR) will be evaluated for injected and non-injected lesions as well as for all target lesions. The ORR will include patients with complete response (CR) or partial response (PR). The DCR will include patients with CR, PR, or stable disease. The ORR and DCR will be determined by Investigator using RECIST v1.1.

Unless otherwise specified, all efficacy analyses will be performed by:

- Lesion type – injected, non-injected lesions, all target lesions

- Evaluation criteria – RECIST v1.1
- Study Phase – Phase 1 by dose groups, Phase 2 by analysis groups

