Target Lesions	Non-target Lesions	New Lesions	Overall Response
CR	CR	No	CR
CR	Non-CR/non-PD	No	PR
CR	Not evaluated	No	PR
PR	Non-PD or not all evaluated	No	PR
SD	Non-PD or not all evaluated	No	SD
Not all evaluated	Non-PD	No	NE
PD	Any	Yes or No	PD
Any	PD	Yes or No	PD
Any	Any	Yes	PD

Source: ([Eisenhauer, Therasse et al. 2009](#))

CR = complete response; NE = not evaluable; PD = progressive disease; PR = partial response; SD = stable disease.

Immune-related RECIST

irRECIST is a modification of RECIST v1.1 which requires confirmation of initial PD per RECIST v1.1 with an additional scan obtained at least 4 weeks later that also meets the criteria of PD progression per RECIST v1.1. In determining whether or not PD is confirmed per irRECIST, the investigator should consider all target and non-target lesions as well as any incremental new lesion(s).

The following are scenarios where PD is confirmed at repeat imaging if ANY of the following occurs by irRECIST:

- Tumor burden remains $\geq 20\%$ and at least 5 mm absolute increase compared to nadir
- Non-target disease resulting in initial PD is qualitatively worse
- New lesion resulting in initial PD is qualitatively worse

- Additional new lesion(s) since last evaluation
- Additional new non-target progression since last evaluation

The following are scenarios where PD is not confirmed at repeat imaging if ALL of the following occur by irRECIST:

- Tumor burden is $< 20\%$ or < 5 mm absolute increase compared to nadir
- Non-target disease resulting in initial PD is stable or qualitatively improved
- New lesion resulting in initial PD is stable or qualitatively improved
- No incremental new lesion(s) since last evaluation
- No incremental new non-target progression since last evaluation

The rationale of the modification is to address observed *pseudoprogression* as well as late responses that are expected with immunotherapy. Guidance for continued imaging and treatment following an initial determination of PD per RECIST v1.1 is provided in the protocol in Section [10.4.1](#).

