9.6.6 Progression-Free Survival

The progressive-free survival (PFS) is defined as the period of time from baseline to confirmed PD or death. Administration of palliative radiation therapy will be considered clinical progression for the purposes of determining PFS. The proportion of patients who had PFS at the end of the study will be summarized and PFS will be analyzed by Kaplan-Meier method; 95% confidence interval for the median will be provided. Overall survival (OS) is defined as the period of time from baseline to death, and analysis of OS will also be provided similarly as PFS.

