Progressive disease (PD): At least 20% increase in the sum of diameters of target lesions, taking as reference the smallest prior sum of diameters in the trial (this includes the baseline sum if that is the smallest in the trial). In addition to the relative increase of 20%, the sum must also demonstrate an absolute increase of least 5 mm.

Stable disease (SD): Neither sufficient shrinkage to qualify for PR nor sufficient increase to qualify for PD, taking as reference the smallest sum of diameters while in the trial.

Non-target lesion response assessment

Complete response (CR): Disappearance of all non-target lesions and normalization of tumor marker level. All lymph nodes must be non-pathological in size (<10 mm short axis).

Non-CR/Non-PD: Persistence of 1 or more non-target lesion(s) and/or maintenance of tumor marker level above the normal limits.

Progressive disease (PD): Unequivocal progression of existing non-target lesions. (Note: the appearance of 1 or more new lesions is also considered progression).

New lesion assessment

At each post baseline imaging timepoint, an evaluation of the presence of new lesions (yes/no) is made. The lesions are recorded as new lesions and not target or non-target lesions.

Lymph nodes must be a new lesion and measure at least 10 cm by short diameter to qualify as a new lesion overall response assessment.

A lesion identified on a follow-up study in an anatomical location that was not scanned at baseline is considered a new lesion.

Overall response assessment

Overall response assessment is based on target lesion response, non-target lesion response and new lesions and is listed in Figure 1 below.

Figure 1: Overall Response Definitions Using RECIST 1.1

Target Lesions	Non-target Lesions	New Lesions	Overall Response
CR	CR	No	CR
CR	Non-CR/non-PD	No	PR
CR	Not evaluated	No	PR

PR	Non-PD or not all evaluated	No	PR
SD	Non-PD or not all evaluated	No	SD
Not all evaluated	Non-PD	No	NE
PD	Any	Yes or No	PD
Any	PD	Yes or No	PD
Any	Any	Yes	PD

CR = complete response; NE = not evaluable; PD = progressive disease; PR = partial response; SD = stable disease.

Approved

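### SAP 9.6 names only target-lesion growth as the criterion for confirming progression, against SAP Appendix 1 and Protocol Appendix 6; applied literally, it omits or delays PFS events in clinically stable patients who progress by new or non-target lesions

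*SAP*

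**What the plan says.** SAP 9.6 marks the immune-related criteria as not implemented but keeps their confirmation step: "Therefore, RECIST v1.1 will be used with the following adaptations (Appendix 1"). Under that step, "both the initial lesion assessment and lesion assessment on the confirmatory scan must meet PD criteria", with a parenthesis giving the criterion as an increase of at least 20% in the sum of diameters. Protocol 8.2.1.1 has the same sentence and parenthesis. SAP 9.6 then adds an exemption: "Patients that are deemed clinically unstable are not required to have repeat imaging for the confirmation of PD".

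SAP Appendix 1 defines PD more widely. Target-lesion PD needs a 20% rise over the smallest prior sum and an absolute rise of at least 5 mm. Non-target PD is "Unequivocal progression of existing non-target lesions. (Note: the appearance of 1 or more new lesions is also considered progression"). The overall-response table gives PD whenever a new lesion is present, whatever the target and non-target results.

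Protocol Appendix 6 lists five scenarios, any one of which confirms PD at repeat imaging. One of them is "New lesion resulting in initial PD is qualitatively worse".

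SAP 9.6.6 says PFS "is defined as the period of time from baseline to confirmed PD or death", and adds: "Administration of palliative radiation therapy will be considered clinical progression for the purposes of determining PFS". SAP 4.0 labels the endpoint as PFS per RECIST v1.1. SAP 9.6.5 ends duration of response at PD or death, without requiring the PD to be confirmed.

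**The concern.** A programmer working from SAP 9.6 finds one stated criterion for confirming PD, and it concerns target lesions only. SAP Appendix 1 cannot fill the gap, because it mentions the immune-related criteria but does not reproduce their confirmation scenarios.

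This trial injects lesions directly, and both injected and non-injected response are Phase 2 primary objectives. Injected targets may shrink or hold steady while disease appears elsewhere, which would show that the systemic effect has failed. A rule that looks only at target diameters is least sensitive to that pattern, so Kaplan-Meier PFS could look longer than the recorded disease course supports.

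**Working it through.** **Step 1. The rules side by side**

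| Route to progression | SAP 9.6 parenthesis | SAP Appendix 1 (is it PD?) | Protocol Appendix 6 (is PD confirmed?) |
|---|---|---|---|
| Target growth of at least 20% | Yes, no absolute minimum stated | Yes, with at least 5 mm | Yes, with at least 5 mm over nadir |
| Non-target progression | Not named | Yes | Yes, if qualitatively worse |
| New lesion | Not named | Yes | Yes, if qualitatively worse |
| Further new lesions | Not named | Yes | Yes |
| Further non-target progression | Not named | Yes | Yes |

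**Step 2. One patient through the three rules.** Take a clinically stable patient whose target lesions are shrinking. The first scan shows a new lesion. The repeat scan, 4 weeks later or more, shows it larger. SAP Appendix 1 gives PD at the first scan. Protocol Appendix 6 confirms it at the second. Under the literal 9.6 criterion neither scan qualifies, and the patient stays event-free in the PFS analysis until the target sum grows, palliative radiation is given, or death occurs.

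**Step 3. The 5 mm minimum.** A 20% rise is less than 5 mm whenever the nadir sum is below 5 / 0.20 = 25 mm. For those patients the parenthesis alone is looser than Appendix 1, which works in the opposite direction. Since 9.6 cites Appendix 1, this is a smaller matter than the missing routes.

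**Step 4. Size (illustration only).** The plan has no PFS assumption to reproduce. Inputs:
- Median m = 4.1 months, the pembrolizumab every-3-weeks result in ipilimumab-naive melanoma cited in Protocol 2.1.1. It is not a design input of this trial.
- Share f of first events that are new-lesion or non-target PD only: assumed.
- Hazard μ of the later event that does count: assumed.

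With exponential times, λ = ln 2 / 4.1 = 0.169 per month.
- If affected patients are censored at that progression, the median is m / (1 − f). At f = 20%: 4.1 / 0.8 = 5.1. At f = 50%: 4.1 / 0.5 = 8.2.
- If they are followed to a later counted event, solve exp(−λt) + fλ[exp(−λt) − exp(−μt)] / (μ − λ) = 0.5. When μ = λ the second term is fλt·exp(−λt).
- If they are counted only at death, put μ = ln 2 / (median post-progression survival), assumed to be 6 to 24 months.

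Median PFS in months, against a true 4.1:

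| f | Censored | Later event, μ = λ | μ = 2λ | μ = 3λ | Counted only at death |
|---|---|---|---|---|---|
| 20% | 5.1 | 5.0 | 4.7 | 4.6 | 5.2–5.6 |
| 30% | 5.9 | 5.6 | 5.0 | 4.8 | 5.9–6.8 |
| 50% | 8.2 | 6.8 | 5.7 | 5.2 | 7.5–11.0 |

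The direction is the same in every cell. The size depends wholly on f and μ.

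**The case against.** The strongest reply is that the parenthesis is shorthand for the target-lesion criterion. SAP 9.6 cites Appendix 1, where "the appearance of 1 or more new lesions is also considered progression" and where the 5 mm minimum appears. SAP 4.0 bases imaging endpoints on investigator evaluation, and Protocol Appendix 6 told investigators to weigh target, non-target and new lesions when confirming PD. Nothing shows that an investigator's recorded new-lesion PD would be overridden by a diameter calculation.

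That stands as a reason not to assert that the reported PFS will be wrong. It does not remove the conflict. The parenthesis is presented as part of an adaptation of RECIST, so it reads as the operative rule, and the SAP contains no other confirmation rule.

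A reader might infer that new-lesion or non-target progression can never become a PFS event. The documents do not support that: clinically unstable patients need no repeat scan, and palliative radiation, later target growth or death each still give an event. A reader might also infer that duration of response is inflated to the same degree. SAP 9.6.5 ends it at PD, not confirmed PD, so it is affected only if the 9.6 definition is carried over.

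It is also fair that the consequence is limited. PFS is secondary, no hypothesis testing is planned, and Phase 2 collection of PFS stopped at Amendment 9. The SAP nevertheless plans a Kaplan-Meier PFS analysis, so the rule still governs data already collected.

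**Conclusion.** The stated criterion is wrong as written. It conflicts with SAP Appendix 1 on what progression is and with Protocol Appendix 6 on what confirms it; a confirmed-PD event also sits awkwardly with the RECIST v1.1 label in SAP 4.0. If it is applied literally, events are omitted or delayed for clinically stable patients who progress only by new or non-target lesions, and that gap can only lengthen PFS.

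That PFS will be overstated is a conditional conclusion. It depends on the parenthesis being programmed instead of the investigator's overall assessment being used, and the documents do not settle which will happen.

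No figure for the bias can be derived from the documents. The illustrative shift from 4.1 months to about 5 to 8 months or more rests on an assumed share and assumed later events. It is smaller if later events come soon. The 11.0-month extreme counts half of first events only at death, ignores every other route to an event, and should not be relied on. The 4.1-month reference does not represent the HNSCC or anti-PD-1-experienced groups.

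**What to change.** In SAP 9.6, replace the parenthesis with: *PD by any route in Appendix 1 (target lesions at least 20% and at least 5 mm over nadir, unequivocal non-target progression, or a new lesion)*.

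Wherever confirmation is kept for the analysis, use the any-of list in Protocol Appendix 6 as far as the recorded investigator assessments allow. Some of its scenarios need a judgement that disease is qualitatively worse, and the documents do not show that the CRF captured it. State what is done where it was not captured.

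Apply one PD definition to PFS and duration of response, consistent with the RECIST v1.1 label in SAP 4.0. In the same edit, state whether the event is dated at the first or the confirmatory scan, and how PD without a repeat scan is handled.

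Because the fix leans on SAP Appendix 1, also correct its new-lesion threshold for lymph nodes. It reads 10 cm there, against 10 mm in Protocol Appendix 6 and 1.0 cm elsewhere in the same SAP appendix.

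The cost is a few sentences in the SAP and one derivation rule, applied to assessments already recorded. The change concerns the analysis only and does not touch treatment decisions.

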In Phase 2, ORR and DCR will be evaluated, which will comprise all lesions as well as for injected and non-injected lesions independently. The ORR will include patients with CR or PR. The DCR will include patients with CR, PR, or stable disease. The ORR and DCR will be determined using both RECIST v1.1 and irRECIST. Details of analyses will be provided in a separate study statistical analysis plan.

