3.2.1 Primary Objectives

- To assess the tumor response both locally and systemically including:
 - Treatment response of the injected lesion(s) (local response)
 - Treatment response of the non-injected lesion(s) (systemic response)
 - Treatment response of all lesions

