9.6.1 Objective Response Rate

The ORR is the proportion of patients who achieve a response of either CR or PR. ORR will be summarized and 95% Clopper Pearson confidence interval will be reported for each dose or analysis group.

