APPENDIX 1 RECIST V1.1**Response Definition**

Assessments will use RECIST 1.1 guidelines, which are included in the Study Reference Manual, and study specific modification of the RECIST 1.1 guidelines referred to as immune related RECIST 1.1 (irRECIST 1.1).

RECIST 1.1

Baseline selection of lesions

All lesions are measured by long axis and short axis (perpendicular to the long axis). At baseline, all tumor lesions are identified as either target lesions or non-target lesions and will be evaluated at baseline and every post baseline imaging timepoint.

Target lesions: Minimal size of 1.0 cm by long axis unless a lymph node which must be a minimal size of 1.5 cm by short axis. Superficial lesions must measure at least 10 mm in long diameter and be measurable by calipers to qualify as target lesions. Maximum target lesions are 5 with a maximum of 2 lesions per organ representative of all involved organs.

Non-target lesions: Radiographically visible but do not meet size qualification of target lesions. Lymph nodes must measure at least 1.0 cm by short diameter to qualify as non-target lesions (if smaller considered non-pathologic). Excess target lesions (> 5 overall or 2 per organ) are followed as non-target lesions.

Baseline measurement of lesions

At baseline, the sum of the long diameters of all target lesions (5 lesions total with maximum of 2 lesions per organ representative of all involved organs), is calculated. The sum is referred to as the sum of diameters (SOD) for the baseline timepoint. All other lesions should be identified as non-target lesions and be recorded at baseline.

Postbaseline radiographic response assessment

At each post baseline imaging timepoint, the long axis diameter of all target lesions are measured and recorded. A response of the target lesions is assessed by determination of the overall SOD of the lesions (SOD for that imaging timepoint). A response for each baseline non-target lesion is determined and recorded. The presence of any new lesions are recorded (of note a lymph node must measure at least 1.0 cm by short axis diameter to qualify as a pathologic lesion).

Target lesion response

Complete response (CR): disappearance of all target lesions. Any pathological lymph nodes (whether target or non-target) must have reduction in short axis to < 10 mm.

Partial response (PR): At least a 30% decrease in the sum of diameters of target lesions, taking as reference the baseline sum of diameters.

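### SAP 9.6 specifies ORR and DCR on target lesions where the primary objective says all lesions, so it is unclear whether new-lesion and non-target progression count against response

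*SAP*

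**What the plan says.** SAP 9.6 states that ORR and DCR will be evaluated for "injected and non-injected lesions as well as for all target lesions". The list at the end of 9.6, which governs every efficacy analysis unless something else is specified, gives the same three lesion types. The same section adds "The ORR and DCR will be determined by Investigator using RECIST v1.1".

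SAP 9.6.1 then says "The ORR is the proportion of patients who achieve a response of either CR or PR". SAP 9.6.3 defines DCR in the same style, adding stable disease. Neither subsection names a lesion set or says whether the categories are those of target-lesion response or of overall response.

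Other places describe the third lesion set differently. SAP 2.0 refers to the combination of all lesions. The Phase 2 primary objective in SAP 3.2.1 includes "Treatment response of all lesions". Protocol 8.2.1.1 says "ORR and DCR will be evaluated, which will comprise all lesions as well as for injected and non-injected lesions independently".

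SAP Appendix 1 contains two constructs that use the same labels. Target-lesion PR is "At least a 30% decrease in the sum of diameters of target lesions" relative to baseline. Separately, "Overall response assessment is based on target lesion response, non-target lesion response and new lesions".

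**The concern.** ORR per RECIST v1.1 is the Phase 2 primary endpoint of an open-label, non-randomized trial, so its definition needs to be unambiguous. None of the three lesion types listed in 9.6 is the all-lesion response that the primary objective calls for. A programmer who follows 9.6 as written could classify patients on the sum of target diameters alone. A patient whose target lesions shrink by 30% while a new lesion appears would then be entered as PR, although Appendix 1 Figure 1 classifies that assessment as PD. The same applies to DCR when target disease is stable.

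The substitution is also undeclared. SAP 1.0 says that objectives not being evaluated are italicized and tagged as not implemented, and the all-lesion primary objective carries no tag.

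**Working it through.** No stated figure in the plan is in dispute. The check is mainly a comparison of text, followed by the direction and scale of the possible effect.

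**1. Lesion sets side by side**

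| Place | Third lesion set, besides injected and non-injected |
|---|---|
| Protocol 8.2.1.1 | all lesions |
| SAP 2.0 | all lesions combined |
| SAP 3.2.1 (primary objective) | all lesions |
| SAP 9.6, ORR/DCR sentence | target lesions only |
| SAP 9.6, lesion-type list | target lesions only |

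**2. Does invoking RECIST v1.1 settle it?** Not fully. Appendix 1 sets out target-lesion response (CR, PR, SD, PD from target measurements) and overall response (target, non-target and new lesions combined through Figure 1). Both are part of RECIST v1.1 as the SAP presents it. The wording of 9.6 matches the first, and nothing in 9.6.1 to 9.6.3 directs the reader to the second.

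**3. Where the two differ.** In Figure 1, any new lesion gives overall PD, and so does non-target PD, whatever the target response. The appendix also says in its non-target section that "the appearance of 1 or more new lesions is also considered progression".

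**4. Direction.** Every Figure 1 row ending in overall CR or PR has target CR or PR. The only row ending in overall SD has target SD. So every overall responder is also a target-lesion responder, and the same holds for disease control. With d the number of patients who qualify on target lesions but never on overall response, in a group of n:

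- target-lesion rate − overall rate = d/n ≥ 0.

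A patient with an overall CR or PR on an earlier scan who later develops a new lesion is a responder under both readings and does not contribute to d.

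**5. Size per patient.** One such patient adds 100/n percentage points: 4.0 at n = 25, 2.0 at n = 50 and 1.7 at n = 60, the planned cohort sizes. Final tables use rearranged analysis groups by dose (SAP 2.0 and 9.11), with Phase 1 patients pooled into the melanoma groups, so the actual n will differ. The documents do not give d.

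**6. Scale, using the Cohort 1 design as illustration only.** Inputs from SAP 5.0: n = 60, null 35%, alternative 55%, one-sided 0.05, power above 90%.

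- Plan's figure first: the smallest r with P(X ≥ r | 60, 0.35) ≤ 0.05 is 28. Type I error is 0.041 and power P(X ≥ 28 | 60, 0.55) is 0.923, consistent with the stated power.
- Assumption: overall ORR is exactly 35%, and a further share m of patients has target CR or PR but overall PD at every such assessment. Then P(X ≥ 28 | 60, 0.35 + m) is:

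| m (assumed) | Probability of at least 28/60 on a target-only count |
|---|---|
| 0 | 0.041 |
| 2% | 0.080 |
| 5% | 0.178 |
| 10% | 0.447 |

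- On the estimate itself, 28/60 = 46.7% (95% Clopper-Pearson lower bound 33.7%). Reclassifying one, two or three patients gives 45.0%, 43.3% or 41.7% (lower bounds 32.1%, 30.6% and 29.1%).

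These figures apply only under the target-only reading. SAP 9.0 plans no hypothesis test, so the tail probabilities show scale and are not an error rate of the trial.

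**The case against.** The strongest reply is that the SAP never adopts a target-only rule. Section 9.6 opens with standard RECIST v1.1 as the primary evaluation and leaves ORR and DCR to the investigator under those criteria. SAP 4.0 names the endpoint as ORR per RECIST v1.1 and refers to the overall response assessment by the investigator. Under Figure 1, target PR with a new lesion is PD at that assessment. If ORR is built from the investigator's recorded overall response, no bias arises. This stands, and it limits the point. A reader might infer that the primary endpoint has been replaced, or that reported ORR and DCR are biased upward. The documents support neither inference: they contain an inconsistency, and bias follows from only one way of resolving it.

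Three further replies stand in part.

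- SAP 9.6.2 plans a best overall response rate. Its definition does not say which categories count, and it falls under the same lesion-type list, so it does not supply the missing row.
- As of Amendment 9, Protocol Section 8.2 is marked no longer applicable, with ORR and DCR analysis optional on data already collected. The SAP was written to Amendment 8, so the protocol text is relevant background. The firmer contradiction is within the SAP.
- All analyses are descriptive, and no sample-size figure changes.

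The reply does not remove the ambiguity, because Appendix 1 offers a target-lesion CR, PR and SD that fits 9.6 word for word. The PD-confirmation bullet in 9.6 adds to it by citing only the increase in sum of diameters. Protocol 8.2.1.1 has the same bullet, but Protocol Appendix 6 also lists new and non-target lesions as ways to confirm PD under irRECIST, and SAP Appendix 1 omits that list.

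**Conclusion.** The point holds as a defect in the definition of the primary endpoint. SAP 9.6 twice specifies target lesions where SAP 2.0, SAP 3.2.1 and Protocol 8.2.1.1 specify all lesions, and 9.6.1 and 9.6.3 do not say which RECIST construct is meant. A literal application would report a target-lesion rate as the primary ORR and could bias ORR and DCR upward.

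The possible error runs in one direction only and equals d/n. Its size is unknown because d is not in the documents; the 2% to 10% shares used above are assumptions. It would be too strong to say that patients with new lesions will be counted as responders, since the same section points to investigator RECIST v1.1. The wording should be settled before the efficacy tables are programmed.

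**What to change.** - In both places in SAP 9.6 (the ORR/DCR sentence and the lesion-type list), replace the target-lesion item with: *all lesions (overall response per RECIST v1.1, Appendix 1 Figure 1, including non-target and new lesions)*.
- Name that row the primary ORR.
- In 9.6.1 to 9.6.3, state that CR, PR and SD for this row mean overall response.

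It would also help to state how non-target and new lesions enter the injected and non-injected rows, because Protocol 6.2.2.2 and 6.2.2.3 allow a replacement injected lesion to be target, non-target or new.

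The cost is SAP wording. Protocol 8.2 had investigators record response and progression on the case report form before Amendment 9, and the RECIST appendices require new lesions to be recorded at each imaging time point. No new data are needed and no sample-size statement changes.
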